8.1 Subject Disposition

Subject disposition will be summarized by group (frequency and the percentage of subjects) and overall. The following categories will be summarized by number and percentage.

- Screened and screen failures subjects (overall only).
- Enrolled and not enrolled subjects (overall only).
- Subject who are dosed (by group and overall).
- Subject who are not dosed (by group and overall).
- Subject who have completed the study (by group and overall).
- Subjects who discontinued in the treatment period (by group and overall).
- Primary reason for discontinuation (by group and overall).

Subject discontinuation information will be listed.

For subjects enrolled, not enrolled and screen failures, the percentage denominator will be the number of screened subjects. For all other calculations, the percentage denominator will be the number of subjects dosed in each group. For overall, percentages based on the overall number of subjects dosed (safety population).

8.2 Protocol Deviations

The protocol deviations will be categorized and listed by subject.

8.3 Demographics and Baseline Characteristics

Descriptive statistics (sample size (n), mean, median, standard deviation [SD], minimum [Min], and maximum [Max]) will be calculated for continuous variables (age, body mass index [BMI], height, and weight) considering last results (scheduled or unscheduled) obtained prior to the dosing of ELX-02. Frequency counts and percentages will be tabulated for categorical variables (age group, gender, ethnicity and race). All summaries will be presented by group and overall. All demographic characteristics will be listed by subject.

8.4 Renal Function Classification

Subjects will be classified according to their estimated glomerular filtration rate (eGFR) obtained from the Modification of Diet in Renal Disease (MDRD4) study equation (Table 8-1) based on serum creatinine. Cystatin concentrations may be used for data analysis if needed. Subjects' eligibility will be based on screening results and subjects will be assigned at check-in to one of the following groups based on the screening eGFR:

Eloxx Pharmaceuticals

Table 8-1 Classification of Subjects in Groups According to Renal Function

Group	Description	$eGFR (mL/min/1.73 m^2)$
1	Mild decrease in GFR	60-89
2	Moderate decrease in GFR	30-59
3	Severe decrease in GFR	< 30
4	Control (normal) GFR	≥ 90

MDRD4 (4-variable) equation:

eGFR = $175 \times (Scr)^{-1.154} \times (Age)^{-0.203} \times (0.742 \text{ if female}) \times (1.212 \text{ if African American}).$

where: eGFR is expressed as mL/min/1.73 m² of body surface area.

Scr is serum creatinine expressed in mg/dL.

Age is expressed in years

Variables are: serum creatinine, age, gender, and race.

In addition, serum cystatin C will be measured during screening procedures. However, no additional analyses will be performed based on this endogenous glomerular filtration marker.

eGFR and its individual component results will be listed by subject.

8.5 Medical History

Medical history will be listed by subject. The Medical Dictionary for Regulatory Activities (MedDRA®) Version 21.1 will be used to classify all medical history findings by System Organ Class (SOC) and Preferred Term (PT).

8.6 Prior and Concomitant Medications

The use of prior and/or concomitant medications will be monitored throughout the study and listed by subject. The World Health Organization Drug Dictionary (WHO DD) Version Sep2018, format B3 will be used to classify all medication reported during the study.

A summary of prior medications use will be presented. Concomitant medications will be summarized by group and overall. All prior and concomitant medications will be listed by subject.

8.7 Study Drug Administration

The study drug administration details (including treatment received, date and time of administration) will be listed by subject.

Time of dosing will be set equal to the time when the ELX-02 injection is administered to the subject.

9. Safety Analyses

Safety and tolerability of ELX-02 will be evaluated through the assessment of AEs (i.e., seriousness, severity, relationship to the study drug, outcome, duration, and management), local reactions at the injection site, clinical laboratory parameters (biochemistry, hematology, cogulation, and urinalysis), 12-lead electrocardiogram (ECG), vital sign, and physical examination. Laboratory values (hematology, biochemistry, urinalysis, and coagulation), will be summarized overall or according to the group, as appropriate.

Safety data will be summarized, but will not be subjected to inferential analysis.

9.1 Physical Examination Findings

A complete physical examination will be performed at screening. A brief physical examination will be done on Day -1, at check-out on Day 4 and at study exit.

The complete physical examination will include at least the following components: head, eyes, ears, nose, throat (HEENT), neck, chest, lungs, abdomen, musculoskeletal, dermatological, cardiovascular/peripheral vascular evaluation, and general neurological examination.

A brief physical examination includes assessments of the following components: HEENT, chest, lungs, abdomen, musculoskeletal, dermatological, cardiovascular/peripheral vascular, general neurological examination, and areas of note elicited from the subject.

Body measurements will be performed at screening and will include body weight, height measurement, and BMI. Body measurement will be summarized (mean, median, standard deviation [SD], minimum [Min], maximum [Max], and sample size) in demographic tables (safety and PK).

Any abnormal findings judged to be clinically significant will be documented as medical history or as an AE, depending upon time of observation, as appropriate. Any physical examination findings documented as AEs will be included in the AE summaries.

9.2 Adverse Events

Treatment-emergent AEs (TEAEs) and non-TEAEs will be listed. TEAEs will be defined as AEs that occur on or after the date and time of study drug administration. Any AE that first occurs pre-dose but worsens in severity after the first study drug administration will also be considered a TEAE. Non-TEAEs are those that occur prior to the first administration of the study medication and resolved prior to dosing or that first occur prior to the first study drug administration but do not worsen in severity after dosing. TEAEs will be captured during the study until study exit. Adverse events will be followed-up until complete resolution, or until the Principal Investigator or Medical Sub-Investigator judges safe to discontinue follow-up.

The incidence of TEAEs will be summarized using the safety population. The MedDRA® dictionary Version 21.1 will be used to classify all TEAEs reported during the study by SOC and PT.

Eloxx Pharmaceuticals

The relationship of TEAEs will be classified according to the study protocol as certain, probably/likely possible, unlikely, or unrelated (not related) to ELX-02. The severity of TEAEs will be classified according to the study protocol as mild, moderate or severe.

Incidence of subjects who experienced TEAEs (frequency and the percentage of subjects) will be presented for each group and overall by:

- SOC and PT;
- SOC, PT, and relationship;
- SOC, PT, and maximum severity.

Each subject may only contribute once to each of the incidence rates, for a TEAE occurring during the same group, regardless of the number of occurrences; the highest severity or highest relationship will be presented, as appropriate. In each table, the SOC will be presented in descending order of overall incidence rate in terms of frequency of subjects and then in frequency of events (alphabetical order will be used in case of equal rates). For each SOC, PT will be presented the same way.

Number of TEAEs will also be presented by:

- SOC and PT;
- SOC, PT, and relationship;
- SOC, PT, and maximum severity.

Serious adverse events (SAEs) and TEAEs leading to early discontinuation of study drug will be listed separately.

9.3 Laboratory Parameters

Biochemistry will be performed at screening, at check-in on Day -1, and at study exit, following a fasting period of at least 8 hours. The following will be assessed: albumin, alkaline phosphatase (ALP), aspartate aminotransferase (AST), alanine aminotransferase (ALT), urea, calcium, chloride, glucose, phosphorus, potassium, creatinine, sodium, direct bilirubin, indirect bilirubin, total bilirubin, creatine phosphokinase (CPK), and total protein. Considering that indirect bilirubin is calculated from total and direct bilirubin values, indirect bilirubin result would not be available in case of direct bilirubin below the limit of quantification. Serum creatinine will also be measured approximately 24 hours post-dose (Day 2). eGFR will be estimated based on the equation provided in SAP Section 8.4.

Hematology will be performed at screening, at check-in on Day -1, and at study exit. The following will be assessed: complete blood count with differential, hemoglobin, and hematocrit.

Coagulation tests including prothrombin time (PT), activated partial thromboplastin time (aPTT) and international normalized ratio (INR) will be performed at screening, at check-in on Day -1 and at study exit. The following will be assessed: PT/INR and aPTT.

Eloxx Pharmaceuticals

Urinalysis will be performed at screening, at check-in on Day -1, at approximately 24 and 72 hours post-dose, and at study exit. The following will be assessed: macroscopic examination, pH, specific gravity, protein, glucose, ketones, bilirubin, occult blood, nitrite, urobilinogen, and leukocytes. Unless otherwise specified, microscopic examination will be performed on abnormal findings and these results will be listed only.

Urine samples collected for PK assessment from dosing to 24 hours post-dose will also be used for analysis of creatinine, in order to calculate creatinine clearance (corrected for BSA), along with the serum creatinine value measured 24 hours post-dose. The total amount of creatinine excreted over 24 hours (addition of the 0-3, 3-6, 6-9, 9-12, 12-18, 18-24-hour post-dose time intervals) and the total volume of urine excreted over this 24-hour period will allow calculating creatinine clearance over 24 hours using the following formula:

Corrected CrCl = $\underline{\text{Ucr}}$ x $\underline{\text{Uvol}}$ x $\underline{\text{1.73}}$ where:

Corrected CrCl is expressed as mL/min/1.73 m² of BSA
Ucr is urine creatinine expressed in mg/dL
Uvol is the volume of urine expressed in mL
Scr is serum creatinine expressed in mg/dL
Time is expressed in minutes
BSA is calculated based on the height measured at screening and body
Weight measured on Day -1, and expressed in m².

Urine samples for early markers of renal injury (KIM-1 and clusterin) and for creatinine will be collected prior to dosing, at approximately 12, 24, 36, and 48 hours post-dose, as well as on Day 8.

Listings of all clinical laboratory results, including those unscheduled, will be provided with the abnormal values flagged with "L" for low and "H" for high for continuous parameters, and "A" for abnormal for categorical parameters.

Descriptive statistics (mean, median, SD, Min, Max, and sample size) for each clinical laboratory test (continuous variables) will be presented by group and overall for screening, check-in on Day-1 and study exit. Unscheduled results will not be included in the summary tables except for baseline calculation if applicable. Change from baseline descriptive statistics for study exit will be presented. Baseline will be defined as the last results (scheduled or unscheduled) obtained prior to the administration of ELX-02. For categorical variables (urinalysis tests), the number of subjects (frequency and percentage) will be tabulated for each individual result (e.g., negative, positive, trace). Results from repeat tests will not be included in the summary statistics unless the repeat was required (and documented as such) due to technical reasons or an invalid initial result.

A summary table of shifts from baseline to study exit measurements will be provided. Baseline will be defined in the same manner as described in the preceding paragraph for continuous variables. The shift tables will include normal, low, and high relative to the laboratory reference ranges (or normal-abnormal for categorical variables). Results from repeat tests will not be included in the summary statistics unless the repeat was required (and documented as such) due to technical reasons or an invalid initial result.

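### SAP 9.3 names study exit as the only post-dose visit in the by-group tables for continuous laboratory tests, so the 24-h serum creatinine and the 12-48 h renal injury markers enter no specified summary

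*SAP*

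**What the plan says.** SAP 9.3 plans three by-group outputs for continuous laboratory tests.

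- Descriptive statistics "will be presented by group and overall for screening, check-in on Day-1 and study exit".
- Change from baseline: "Change from baseline descriptive statistics for study exit will be presented".
- Shifts: "A summary table of shifts from baseline to study exit measurements will be provided". For continuous tests, "The shift tables will include normal, low, and high relative to the laboratory reference ranges".

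The same section schedules a serum creatinine at about 24 h (Day 2). It also schedules KIM-1, clusterin and urine creatinine before dosing, at about 12, 24, 36 and 48 h, and on Day 8.

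The early values have other places in the plan. SAP 9.3 states "Listings of all clinical laboratory results, including those unscheduled, will be provided with the abnormal values flagged". The 0-24 h creatinine clearance is calculated from the pooled urine "along with the serum creatinine value measured 24 hours post-dose". For eGFR, SAP 8.4 says "eGFR and its individual component results will be listed by subject".

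**The concern.** ELX-02 is an aminoglycoside cleared mainly by the kidney, and the study doses people whose kidneys are already impaired. Protocol 5.2.1 counts impaired renal function among the conditions that raise the risk of aminoglycoside nephrotoxicity. The 24-h serum creatinine and the 12-48 h markers are the scheduled measurements that could show an early, passing renal change. If the by-group tables start at exit, a change that has resolved by then and was not judged an adverse event can be found only by reading listings. The secondary objective is safety and tolerability across the renal function groups, so a by-group view is what the reader of the report will look for.

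**Working it through.** No power or error-rate arithmetic applies. The check sets collection times against the times named for summary.

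**Step 1. Post-dose times collected and named**

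| Measurement | Collected post-dose | Named for by-group descriptives |
|---|---|---|
| ECG (SAP 9.5) | 2 h, Day 4, exit | all: 3 of 3 |
| Vital signs (SAP 9.4) | 2, 4, 24, 48 h, Day 4, exit | all but Day 4: 5 of 6 |
| Serum creatinine (SAP 9.3) | 24 h, exit | exit: 1 of 2 |
| KIM-1, clusterin, spot urine creatinine (SAP 9.3) | 12, 24, 36, 48 h, Day 8 (exit) | exit: 1 of 5 |

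For ECG and vital signs, change from baseline is planned for post-dose measurements in general. For laboratory tests it is planned for exit alone. The 24-h serum creatinine therefore enters 0 of the 3 laboratory outputs. The rule that keeps unscheduled results out of the tables does not explain this, because the sample is scheduled.

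**Step 2. Size**

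- Serum creatinine: 1 of 2 post-dose values per subject is untabulated. With 24 subjects that is 24 of 48, and with 26 subjects it is 26 of 52.
- Timing: exit is 168 ± 24 h, so 144 to 192 h. The first tabulated post-dose creatinine comes 144 − 24 = 120 h to 192 − 24 = 168 h after the 24-h sample. Protocol 9.11 allows exit procedures later still if Day 8 is not possible.

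**Step 3. Do the other uses of the values fill the gap?**

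- Creatinine clearance uses the 24-h serum value, but no by-group table of it is specified. The urine is collected only from 0 to 24 h after dosing, so it has no baseline to change from.
- eGFR is planned as a by-subject listing.
- KIM-1 and clusterin either count as continuous laboratory tests, and then only exit is tabulated, or they do not, and then no table is specified for them. The early values are left out either way.

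**Step 4. Would adding 24 h to the shift table be enough?**

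Solve the MDRD4 equation for creatinine, with f the product of the sex and race factors:

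Scr = (175 × Age^−0.203 × f / eGFR)^(1/1.154)

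At eGFR 30, the upper boundary of the severe group, ages 18 to 80:

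| | f | Scr (mg/dL), age 18 to 80 |
|---|---|---|
| Men | 1 | 2.77 to 2.13 |
| Women | 0.742 | 2.14 to 1.65 |
| Men, race factor | 1.212 | 3.28 to 2.52 |
| Women, race factor | 0.742 × 1.212 | 2.53 to 1.95 |

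The lowest value is 1.647 mg/dL. The documents give no reference range. Under an assumed upper limit of normal anywhere up to 1.64 mg/dL, a subject with eGFR below 30 is above the limit at the measurement used for grouping. A higher limit would leave some women near the boundary in the normal category. Most severe-group subjects are therefore probably High at baseline, and a further rise of any size leaves them High. For them a shift table says little at any visit, and the size of the change is what informs.

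**The case against.** Three points are made against this.

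First, the visit list may not be meant as complete. SAP 9.4 omits the scheduled Day 4 vital signs from its descriptive list, SAP 9 promises laboratory summaries overall or by group as appropriate, and the table shells are in a separate document that is not available. This leaves room for more tables but plans none. The sentence in SAP 9 names no visit and speaks of hematology, biochemistry, urinalysis and coagulation, not of the injury markers. The Day 4 omission is softened by the general change-from-baseline wording in SAP 9.4, which SAP 9.3 lacks.

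Second, nothing is lost. Every laboratory result is listed, serum creatinine with high and low flags. Groups have 6-8 subjects, and a rise judged an adverse event reaches the TEAE tables. This stands and limits the weight of the point.

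Third, the renal risk should not be overstated. Protocol 5.2.1 ties aminoglycoside nephrotoxicity to high and repeated doses as well as to renal impairment. Here each subject gets one dose of 1 mg/kg, and single doses from 0.3 to 7.5 mg/kg have been studied. Protocol 5.1.2 reports no evidence in the completed single-dose studies of an effect on renal function. This stands too.

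**Conclusion.** The gap is real and minor. As SAP 9.3 is written, the 24-h serum creatinine and the 12, 24, 36 and 48 h KIM-1, clusterin and spot urine creatinine values are in no specified by-group summary. This rests on reading the list of visits in SAP 9.3 as it stands. The shells could show otherwise.

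A reader might infer more than the documents support:

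- That the plan contradicts the protocol. Protocol 12.3.2 says laboratory changes from baseline will be evaluated but names no time point.
- That early renal data are discarded. They are listed, and the 24-h creatinine is used for creatinine clearance.
- That every severe-group subject is High at baseline. Groups are set on screening eGFR, while the laboratory baseline is the last result before dosing. Protocol 8.2.1 lets a subject keep the group if eGFR changes on Day -1 without clinical significance, and no reference range is given. Only that most are probably High is defensible.

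Safety is a secondary objective with descriptive analysis only. No PK endpoint or estimate depends on this.

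**What to change.** In SAP 9.3, add to the by-group descriptive and change-from-baseline tables:

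- the 24-h visit for serum creatinine and MDRD4 eGFR;
- the scheduled 12, 24, 36 and 48 h visits for KIM-1 and clusterin.

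For serum creatinine, show percent as well as absolute change. This is a useful addition rather than a necessity, for the reason given in Step 4. Spot urine creatinine can stay in the listing.

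The data are already being collected. The change needs no new sample and no inferential analysis, and it leaves the PK endpoints alone. The cost is some programming and a few more table rows, each resting on only 6-8 subjects per group.

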3.1 General Design

The study is a two-center, Phase 1, open-label, single dose, one-period, four-parallel-group, PK study in subjects with various severities of renal dysfunction and healthy volunteers. The study is intended for filing under the US Food and Drug Administration (FDA) regulations.

A total of approximately 24 to 26 healthy adult male or female volunteers will be enrolled.

Subjects will be enrolled into the trial and assigned to one of the 4 study groups. Six (6) subjects completing the study are targeted for each group of RI subjects (Groups 1 to 3) and 6 to 8 subjects will be included in the control group (Group 4). Attempts will be made to enroll at least two subjects of each gender in each group and subjects with various BMIs.

Subjects will be assigned to one of the following groups:

- Group 1 (Mild): 6 subjects with mildly decreased renal function: eGFR 60 89 mL/min/1.73 m²;
- Group 2 (Moderate): 6 subjects with moderately decreased renal function: eGFR 30 59 mL/min/1.73 m²;
- Group 3 (Severe): 6 subjects with severely decreased renal function: eGFR < 30 mL/min/1.73 m² and not requiring dialysis.
- Group 4 (Control): 6-8 healthy subjects with normal renal function: eGFR $\geq 90 \text{ mL/min}/1.73 \text{ m}^2$;

Group 1 (Mild) and Group 2 (Moderate) will be dosed first, in parallel, with an interim analysis performed (refer to Section 7).

Subjects with normal renal function (Group 4) will be matched with renally impaired (RI) subjects by age (\pm 10 years), gender, and BMI (\pm 15%). A mean matching procedure will be performed. Therefore 6 subjects completing the study are targeted for each of the RI groups (Groups 1 to 3) and 6 to 8 subjects will be included in the control group (Group 4).

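### The SAP's creatinine summaries cannot show worsening in subjects who start above range, are not comparable across renal groups, and leave out the Day 2 value

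*SAP*

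**What the plan says.** For continuous laboratory tests, SAP 9.3 plans three summary displays.

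- Descriptive statistics (mean, median, SD, minimum, maximum, n), which "will be presented by group and overall for screening, check-in on Day-1 and study exit".
- Change from baseline: "Change from baseline descriptive statistics for study exit will be presented". The scale is not stated, and no percent or fold change is mentioned.
- Shifts: "A summary table of shifts from baseline to study exit measurements will be provided". On the categories, "The shift tables will include normal, low, and high relative to the laboratory reference ranges".

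The same section has serum creatinine measured about 24 hours after dosing (Day 2), but Day 2 is not among the summarised visits. It also says "eGFR will be estimated based on the equation provided in SAP Section 8.4", without defining a change display for eGFR. Individual data are kept: "Listings of all clinical laboratory results, including those unscheduled, will be provided with the abnormal values flagged".

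SAP 3.1 defines Group 3 as "6 subjects with severely decreased renal function", with eGFR below 30 and no dialysis. Group 2 has eGFR 30-59, Group 1 has 60-89, and the control group has 90 or more.

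**The concern.** Three of the four groups are recruited because renal function is reduced, and the classification is computed from serum creatinine. A low/normal/high shift table is informative only for subjects who can cross a limit. A subject above the limit at baseline and again at exit stays in one cell whether creatinine rose by 5% or doubled.

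Change from baseline in mg/dL has a different problem. Creatinine varies roughly as the inverse of GFR, so the same proportional loss of function gives a larger mg/dL change where baseline creatinine is higher. A by-group table of raw changes then mixes drug effect with baseline level, and the pooled overall column averages over both.

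This matters because safety by renal function group is the secondary objective. Protocol 5.2.1 names nephrotoxicity as an aminoglycoside risk that is generally greater when renal function is already impaired. Safety is reported descriptively only, so these tables are what most readers will rely on.

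**Working it through.** The plan gives no figure on this point, so there is none to reproduce. The check inverts the plan's own equation.

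**Inputs from the documents.** MDRD4 (Protocol 9.2, SAP 8.4): eGFR = 175 × Scr^-1.154 × age^-0.203 × 0.742 if female × 1.212 if African American. Group limits are as above. Eligible ages are 18 to 80.

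**Assumptions, not in the documents.** A creatinine upper limit of about 1.0-1.3 mg/dL; illustrative eGFRs within groups (severe 15-30, control 90-120); change from baseline read as an absolute difference.

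**Step 1: implied baseline creatinine.** Scr = (175 × age^-0.203 × sex factor / eGFR)^(1/1.154), where 1/1.154 = 0.8666. The race factor is left out because it only raises the result.

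| eGFR | Man of 60, mg/dL | Woman of 60, mg/dL |
|---|---|---|
| 90 | 0.87 | 0.67 |
| 60 | 1.23 | 0.95 |
| 45 | 1.58 | 1.22 |
| 30 | 2.24 | 1.73 |
| 20 | 3.19 | 2.46 |
| 15 | 4.09 | 3.16 |

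The lowest value possible in Group 3 is at the eGFR 30 boundary for a woman of 80: (175 × 0.4108 × 0.742 / 30)^0.8666 = (53.35 / 30)^0.8666 = 1.65 mg/dL. For a man of 80 it is 2.13. All of Group 3 is therefore above a limit of 1.0-1.3.

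For Group 2 at ages 40 to 75, the range is 0.93 to 1.86 (women) and 1.20 to 2.41 (men), so many start High but not necessarily all. A Group 1 man of 60 lies between 0.87 and 1.23 and may well start Normal.

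**Step 2: effect of an equal relative loss.** If eGFR falls by a fraction L, creatinine is multiplied by k = (1/(1 - L))^0.8666, whatever the baseline. For L = 25%, k = (4/3)^0.8666 = 1.283. For a man of 60:

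- eGFR 90: 0.87 to 1.11, a rise of 0.25 mg/dL (from unrounded values). Normal-to-Normal if the limit is 1.2 or 1.3.
- eGFR 20: 3.19 to 4.09, a rise of 0.90 mg/dL. High-to-High.

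**Step 3: ratio of absolute rises, severe to control.** Each rise is Scr × (k - 1). At equal age, sex and race everything cancels except the baselines, leaving (eGFR control / eGFR severe)^0.8666, which does not depend on L.

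| Control eGFR | Severe eGFR | Ratio of mg/dL rises |
|---|---|---|
| 90 | 30 (boundary) | 2.59 |
| 100 | 25 | 3.32 |
| 90 | 20 | 3.68 |
| 90 | 15 | 4.72 |
| 120 | 15 | 6.06 |

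Because the groups are below 30 and at least 90, the ratio always exceeds 2.59.

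**Step 4: the same check for eGFR.** Absolute change distorts the other way. A 20% loss is 18 units at eGFR 90 and 4 units at eGFR 20.

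**Step 5: the ratio scale.** Post-dose over baseline creatinine is k in every group, so equal relative losses look equal by construction.

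**The case against.** The strongest reply is that the planned displays together do not hide a rise. The change-from-baseline table reports the maximum by group, so a 0.90 mg/dL rise in a severe subject is visible. Absolute creatinine change also enlarges the signal in the group most at risk, so it errs towards detection. With about 24 to 26 subjects, baseline and exit values can be read from the listings. This stands. A reader might infer that renal worsening would go unseen in the severe group; the documents do not support that. What remains is that the shift table says nothing about worsening there, and that the other summary does not let groups be compared.

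Second, no planned decision rests on comparing raw changes between groups: safety is not tested, and each change sits beside its own baseline. That limits the harm to interpretation but does not remove it, since comparison by renal function is the reason for tabulating by group.

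Third, the SAP says only change from baseline, and SAP 1 puts the table shells in a separate document that may settle the scale. This also stands. Absolute difference is the ordinary reading, not a stated rule.

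Fourth, other renal measures exist. The SAP says "Urine samples for early markers of renal injury (KIM-1 and clusterin) and for creatinine will be collected prior to dosing" and at later times, and a 24-hour creatinine clearance is calculated. But SAP 9.3 defines no specific summary for the two markers, and the clearance is a single post-dose value with no baseline. Neither replaces a usable creatinine summary.

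Finally, Protocol 5.1.2 reports no evidence that ELX-02 affected renal function in the completed single-dose studies. Those were in healthy subjects, so this bears on how likely a signal is, not on whether the tables could show one in renal impairment. The 25% loss above is illustrative, not a forecast.

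**Conclusion.** The point holds as a weakness of the summary displays. Under an assumed upper limit of 1.0-1.3 mg/dL, the shift table cannot show creatinine worsening in any of the 6 planned Group 3 subjects or in many of the 6 in Group 2. It still works for control subjects and for mild subjects who start in range. Absolute change shows a rise but inflates the same relative loss in severe against control subjects by at least about 2.6-fold, and by about 2.6 to 6 over the assumed eGFR ranges. That rests on MDRD4 and on equal age, sex and race. The Day 2 creatinine is absent from the summaries; this needs no assumption.

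One might be tempted to quote a single factor such as 3.7. That is the case of eGFR 20 against 90 only, and the documents give no typical values within groups. One might also infer that all renally impaired subjects start High; the equation does not support that for Group 1 or for all of Group 2.

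**What to change.** Keep the shift table. Add to SAP 9.3, for serum creatinine, each subject's post-dose/baseline ratio, using the baseline already defined there. Summarise it by group at Day 2 and at study exit (geometric mean, median, minimum, maximum), and list each subject's largest ratio. The same ratio may be given for eGFR, where absolute change misleads in the opposite direction. State in the SAP that the existing change from baseline is an absolute difference, if that is intended.

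The cost is a few lines of SAP text, one extra table shell and one listing shell. No new samples, visits or data are needed.
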